10.3.1 Definitions

Baseline

Baseline eGFR measurements are the nadir of the eGFR of the measurements on the Screening and Day 1 Visits for those subjects who entered prior to Amendment 1 and the mean of these values for subjects who entered post Amendment 1.

Day 1 is the baseline for vital signs, laboratory values, and other measures unless otherwise specified.

Responder Status

Responders are defined as subjects whose End-of-TP1 (the mean of Week 11 and Week 12) eGFR \geq 90% of baseline and \geq 20 mL/min/1.73 m². The baseline eGFR is defined as the mean of the eGFR values obtained during Screening and the Day 1 Visit.

Loss-of-response at the End-of-TP2 is defined as any 1 of the following 3 conditions:

- End-of-TP2 eGFR (mean of Week 36 and Week 38 eGFR) that is not stable, defined as:

- End-of-TP2 eGFR that is < 90% of the End-of-TP1 eGFR for subjects whose End-of-TP1 eGFR (mean of Week 11 and Week 12 eGFR) is \geq 100% of baseline;
- End-of-TP2 eGFR that is < 90% of baseline for subjects whose End-of-TP1 eGFR is \geq 90% of baseline and < 100% of baseline.
- Allograft failure (defined by allograft nephrectomy, or institution of permanent dialysis, or return to the transplant waitlist for renal transplant, whichever occurs first)
- Subject death by any cause.

10.3.2 Subject Disposition and Characteristics

10.3.2.1 Subject Disposition

The following summaries will be provided:

- The number of subjects in each of the analysis sets defined for this study.
- Subject status, including subjects ongoing, subjects completed, and subjects withdrawn from the study, and primary reason for withdrawal.
- Investigation product status, including premature discontinuation of the investigational product and primary reason for premature discontinuation.

10.3.2.2 Subject Characteristics

The following will be summarized using descriptive statistics or frequency counts, as appropriate:

- Demographic characteristics.
- Relevant medical history.
- Allograft/allograft donor characteristics.
- Diagnosis and disease characteristics.
- Prior and concomitant therapies.

10.3.3 Efficacy Analyses

All efficacy endpoints will be analyzed based on Modified-ITT analysis set. Sensitivity analyses for efficacy endpoints will be based on ITT set.

10.3.3.1 Primary Efficacy Analysis

The primary analysis of the primary efficacy endpoint of loss-of-response at the End-of-TP2, will be based on a logistic regression model. The randomized treatment groups, C1-INH and placebo, will be compared based on the logistic model.

Subjects will be considered to have lost response if they drop-out or are lost to follow-up before the response status at the End-of-TP2 could be determined.

If π is the probability that an individual in a given treatment group will have a loss-of-response at the End-of-TP2, the logistic model assumes that in each treatment group, binary outcome of response status can be described by a model which assumes independence between subjects. Also, the model assumes that all subjects with the same covariate values have the same probability, such that the logit of π is a linear function of the regression coefficients particular to that individual:

$$\text{Logit}(\pi) = \log(\pi/(1-\pi)) = \alpha + \beta_T X_T,$$

where X_T is the indicator variable for treatment (C1-INH=1, placebo = 0).

Please note the stratification factors for randomization are not included in this model as difference in efficacy is not expected based on these strata. However, subjects have been randomized based on these strata of DSA sensitized versus DSA de novo and AMR severity (severe versus all other severities) to ensure balance among these strata.

The odds ratio for C1-INH versus placebo is $\exp(\beta_T)$ based on this model for primary efficacy analysis. The primary hypothesis to be tested is $H_0: \beta_T = 0$ vs $H_1: \beta_T \neq 0$. This will be tested using the Wald statistic derived from maximum likelihood estimation of the logistic model. If this hypothesis is rejected at the 0.05 level of significance and the point estimate of β_T is positive, efficacy will be declared. The logistic model will be used to provide point estimates of the odds ratio and risk difference, with 95% confidence intervals by treatment groups. Summary statistics of proportion of subjects with loss-of-response will also be presented by treatment. If maximum likelihood estimation of the logistic model fails to converge then exact methods for logistic regression will be used for hypothesis and estimation.

Components of loss-of-response at the End-of-TP2 will be summarized by treatment groups in terms of the proportion of subjects with:

- End-of-TP2 eGFR (mean of Week 36 and Week 38 eGFR values) that is not stable, defined as:
 - End-of-TP2 eGFR that is < 90% of the End-of-TP1 eGFR for subjects whose End-of-TP1 eGFR is \geq 100% of baseline,
 - End-of-TP2 eGFR that is < 90% of baseline for subjects whose End-of-TP1 eGFR is \geq 90% of baseline and < 100% of baseline
- All-cause allograft failure (ie, allograft nephrectomy, or institution of permanent dialysis, or return to the transplant waitlist for renal transplant).
- Death by any cause.

Sensitivity analysis of loss-of-response at the End-of-TP2

A sensitivity analysis will be performed to access the possible effect of other factors on the analysis by performing the logistic regression including the stratification variables DSA (sensitized versus de novo) and AMR severity (severe versus all other severities), and possibly other key variables, as covariates in the model. If maximum likelihood estimation of the logistic model fails to converge subgroup analyses determined by the above factors will be performed using exact methods for logistic regression. Summary statistics by covariate levels will also be presented.

Further details of the sensitivity analyses will be specified in the SAP.

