6.1.2 Randomization Procedures

All subjects will receive open-label C1-INH during TP1. Subjects who are eligible for TP2 (ie, responder subjects, as defined in [Section 8.1.3.2](#)) will be assigned to either continued C1-INH or matched placebo in accordance with a computer-generated randomization list. Investigational product assigned in TP2 will be allocated on a 1:1 ratio. The randomization (permuted block) will be stratified on the following factors:

- DSA: sensitized prior to transplantation versus de novo; de novo is defined as the development of DSA after transplantation. In the case of both sensitized and de novo, the subject will be considered sensitized for stratification purposes.
- AMR severity: severe versus non-severe (ie, all other severities); severe is defined as new onset oliguria (<400 cc/24 hours) or anuria with the current episode of AMR.

Treatment assignment will be determined centrally. The randomization list will be generated and managed by the study's IRT external service provider. A detailed user guide for the IRT will be available.

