10.3 Statistical Analyses and Methods

A complete description of the statistical analyses and methods will be available in a statistical analysis plan, which will be finalized before the database is locked.

Unless otherwise stated, efficacy analyses will be based on the modified ITT analysis set for analyses of endpoints defined in TP2. Sensitivity analyses will be based on the ITT set.

Enrolled analysis set will be used for the analysis of endpoints defined over the entire study. Sensitivity analyses of these endpoints will be done with ITT and modified ITT sets.

Safety will be summarized over the entire study, and according to treatment period. Safety will be analyzed for either the RiS analysis set or the RWS analysis set, as appropriate.

All data will be summarized in tables or figures and all ICH-required data in the database will be listed. Unless otherwise specified, continuous variables will be summarized by presenting the number of non-missing observations, mean, standard deviation, median, minimum and maximum. Other descriptive statistics (eg, 25th and 75th percentile, coefficient of variation) will be reported when appropriate. Categorical variables will be summarized by presenting the number of subjects and percentage for each category.

Unless otherwise stated, the statistical model on which inference is based will contain terms for the randomization strata as well as treatment. It is anticipated that subject accrual will be spread thinly across the centers. There will be no pooling of centers for purposes of analysis. Therefore, investigation of center-by-treatment interaction will not be possible.

Unless otherwise specified, all confidence intervals and *P*-values will be two-sided. From a formal inferential perspective, the type I error will be fully allocated to the analysis of the primary efficacy variable, and the selected secondary efficacy variable (ie, all-cause allograft failure after randomization into TP2 and through the Responder Follow-up Period). A serial gatekeeper hierarchical testing strategy will be used to protect the overall type I error rate of 0.050 (two-sided). Statistical significance will be claimed only when the results of the two-sided test favor C1-INH.

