10.3.3.2 Secondary Analyses

Analysis of key secondary endpoint of proportion of all-cause allograft failure at the end of 48 months after enrollment

The primary comparison for the proportion of subjects with all-cause allograft failure at the end of 48 months after enrollment will be based on a logistic regression model. The randomized treatment groups, C1-INH and placebo, will be compared based on the logistic model.

The same logistic model as described for the primary endpoint will also be used for this analysis.

Analysis of components of all-cause allograft failure after enrollment into TP1 through the Responder Follow-up Period (ie, within 48 months after enrollment) will be summarized for the randomized treatment groups and also the non-responder subjects who were not randomized in TP2. The summary will be based on the proportion of subjects with:

- Any event (ie, all-cause allograft failure or death by any cause).
- All-cause allograft failure (defined by allograft nephrectomy, or institution of permanent dialysis, or return to the transplant waitlist for renal transplant);
- Surviving allografts
- Death by any cause

Proportion of subjects with all cause allograft failure will be also summarized by treatment groups at 1 year, 2 years, and 3 years since enrollment.

Analysis of key secondary endpoint of time to all-cause allograft failure through 48 months after enrollment

Treatment group differences will be analyzed with a Cox proportional hazards regression model with randomization strata as covariates. This model will be used to estimate the C1-INH /placebo hazard ratio and two-sided 95% confidence interval. Kaplan-Meier plots of time to failure through the Responder Follow-up Period will be produced.

Subgroup analysis of loss-of-response at the End-of-TP2

Details of subgroup analyses will be provided in the SAP.

The following subgroups, and possibly others to be described in the SAP, will be summarized by treatment group with respect to the proportion of loss-of-response:

- Geographic region: USA, non-USA.
- DSA by randomization strata: sensitized, de novo.
- DSA by classification: HLA class I, HLA class II, both HLA class I and II.
- AMR severity: severe, non-severe (all other severities).
- Type of donor: deceased, living.
- Recipient race: Black, non-Black.
- Recipient sex: male, female.
- Recipient age: < 65 years, \geq 65 years.

Subgroup analysis of all-cause allograft failure at the end of 48 months after enrollment

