4.4 Randomization Procedures and Blinding

Randomization Procedures

All subjects will receive open-label C1-INH during Treatment Period 1. Subjects who are eligible for Treatment Period 2 will be assigned to either continued C1-INH or matched placebo in accordance with a computer-generated randomization list. Investigational product assigned in Treatment Period 2 will be allocated on a 1:1 ratio. The randomization will be stratified on the following 2 factors:

- Donor Specific Antibodies (DSA): sensitized prior to transplantation versus de novo. De novo is defined as the development of DSA after transplantation. In the case of both sensitized and de novo, the subject will be considered sensitized for stratification purposes.
- AMR severity: severe versus non-severe (ie all other severities). Severe AMR is defined as new onset oliguria (< 400 cc / 24 hours) or anuria with the current episode of AMR.

Therefore, there will be a total of 4 strata (2 factors, 2 levels per factor). The randomization will be permuted block within each stratum. Treatment assignment will be determined centrally. The randomization list will be generated and managed by the study's interactive response technology (IRT) external service provider.

The study database will be locked once all the randomized subjects currently in the study complete week 38 visit and re-treatment period as described in [Section 3](#). The study will be unblinded for final analysis of the primary efficacy endpoint.

Maintaining the Blind

Treatment Period 1 is open-label. Treatment Period 2 is double-blind. During Treatment Period 2, the blind will be maintained for investigational site staff, including investigators, subjects, and CSL.

Emergency Unblinding

In emergency situations involving the safety of the subject, the investigator may break the blind using the IRT system. The reason for unblinding the randomization code must be fully documented. Emergency unblinding will be performed using the IRT. Steps for navigating the IRT for emergency unblinding are defined in the IRT manual.

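### The primary and key secondary logistic models leave out the two randomization strata without showing that they are non-prognostic, which makes the unadjusted Wald test conservative to the extent that they are prognostic

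*Protocol*

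**What the plan says.** Protocol 6.1.2 states: "The randomization (permuted block) will be stratified on the following factors". The factors are DSA (sensitized or de novo) and AMR severity (severe or not). SAP 4.4 counts four strata and confirms the method: "The randomization will be permuted block within each stratum".

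Protocol 10.3 sets a default for inference: "Unless otherwise stated, the statistical model on which inference is based will contain terms for the randomization strata as well as treatment". Protocol 10.3.3.1 makes an exception for the primary endpoint. The model has an intercept and a treatment term, tested by the Wald statistic, because "the stratification factors for randomization are not included in this model as difference in efficacy is not expected based on these strata". The next sentence says the strata were used in randomization "to ensure balance among these strata". A strata-adjusted model appears only as a sensitivity analysis, "performing the logistic regression including the stratification variables DSA (sensitized versus de novo) and AMR severity".

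For the key secondary proportion with allograft failure, Protocol 10.3.3.2 says: "The same logistic model as described for the primary endpoint will also be used for this analysis". For time to the same event it says: "Treatment group differences will be analyzed with a Cox proportional hazards regression model with randomization strata as covariates".

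The final SAP was written after termination with 13 subjects randomized. It drops all formal testing (SAP 4.2.1.3 and 7.3).

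**The concern.** The reason given most naturally denies a treatment-by-stratum interaction. It could also be read as a remark about outcome. On neither reading does it show that the strata are unrelated to loss of response, and the documents give no data on that. Balancing on a factor helps inference only if the factor is prognostic, so using the strata for balance and then ignoring them needs a reason about prognosis.

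The exception in 10.3.3.1 does not contradict the default in 10.3, which allows exceptions. The treatment of allograft failure is uneven, though. The Cox model keeps the strata. The logistic model for the same outcome drops them on the strength of a sentence written for loss of response, and no adjusted version of it is named.

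At stake is lost power and a somewhat wide confidence interval. False-positive risk is not raised.

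**Working it through.** **Reproducing the plan's power.** Inputs from Protocol 10.1.1: 30 per arm, 0.75 vs 0.30, two-sided alpha 0.05, no strata. With mean rate 0.525, the pooled chi-square approximation gives

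z = [0.45·√30 − 1.96·√(2·0.525·0.475)] / √(0.75·0.25 + 0.30·0.70) = (2.465 − 1.384)/0.630 = 1.714, so power is 95.7%.

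The likelihood ratio chi-square gives 94.5%, and exact enumeration of the unadjusted Wald test gives 95.5%. The stated figure of about 95% holds.

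**Why omission is conservative.** With balance inside strata, the variance of the difference depends on the within-stratum variance Σ w·p(1−p). The unadjusted model uses p̄(1−p̄). Example under the null, assuming 50% sensitized and only DSA prognostic with OR 5, mean rate 0.525:

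- The stratum rates are 0.335 and 0.715.
- The within-stratum variance is 0.2131, against 0.525·0.475 = 0.2494, a ratio of 0.855.
- The Wald statistic then has SD √0.855 = 0.924, and large-sample type I error is 2·[1 − Φ(1.96/0.924)] = 3.4%.

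At N=60, simulation gives 3.8%.

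**Simulation.** The documents do not give prognostic strength, prevalence or block size. Assumed: N=60, blocks of 4, 50% sensitized, 25% severe, stratum effects additive on the logit scale, arm rates fixed at the stated marginal values, 40,000 trials per main scenario. The comparator is CMH over the strata, pooling severe and non-severe within a DSA level when either has fewer than 5 randomized subjects. Entries are unadjusted Wald / CMH, in %. The OR applies to each factor unless stated.

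| Stratum effect | Type I error | 0.75 vs 0.30 | 0.65 vs 0.30 |
|---|---|---|---|
| OR 1 | 5.0 / 5.0 | 95.5 / 95.3 | 80.1 / 79.9 |
| OR 2 | 4.6 / 5.0 | 95.9 / 96.1 | 80.0 / 80.7 |
| OR 3 | 4.0 / 5.0 | 96.1 / 96.8 | 81.0 / 82.9 |
| OR 5 | 3.1 / 4.9 | 96.9 / 98.0 | 81.9 / 86.3 |
| DSA only, OR 5 | 3.8 / 5.1 | 96.4 / 97.2 | 81.0 / 83.8 |
| Severity only, OR 5 | 4.1 / 4.8 | 96.3 / 96.7 | 80.6 / 82.5 |

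The Monte Carlo standard error is about 0.11 point at 5%, 0.10 at 96% and 0.20 at 80%.

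**Key secondary.** At the planned failure rates (0.75 vs 0.25): 98.8 / 99.0 at OR 3 and 99.1 / 99.4 at OR 5. If placebo graft survival is 40%, the top of the range in Protocol 10.1.2 (failure 0.60 vs 0.25): 81.4 / 83.6 at OR 3 and 82.4 / 86.8 at OR 5.

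**With 10% severe, at 0.65 vs 0.30:** 80.1 / 80.1 at OR 1, 79.7 / 80.2 at OR 2, 80.9 / 82.3 at OR 3, 81.6 / 84.4 at OR 5.

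**Source of the effect.** In separate runs (20,000 trials), under simple randomization the unadjusted test stays at 4.9% to 5.4%. At N=400 with stratified blocks (6,000 trials) it is 3.6% at OR 3 and 2.6% at OR 5. The conservatism therefore comes from ignoring the blocking and is not a small-sample artefact.

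**Risk-difference interval at the planned effect, unadjusted vs Mantel-Haenszel.** Mean width is 0.443 vs 0.424 at OR 3 (ratio 1.04) and 0.443 vs 0.410 at OR 5 (ratio 1.08). Coverage is 94.8% vs 93.6% and 95.6% vs 93.9%.

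**The case against.** The unadjusted model is a disclosed and valid choice. At the planned effect the loss is 0.2 point at OR 2, 0.7 at OR 3 and 1.1 at OR 5, from a base above 95%. The larger losses need assumptions the documents do not supply. A low share of severe cases is plausible, because only Treatment Period 1 responders with eGFR of at least 20 are randomized and more than two weeks of dialysis at Screening is exclusionary. The weaker-effect figures hold N at 60, although Protocol 10.1.3 plans a sample size re-estimation that cannot reduce N. Adjustment is already a sensitivity analysis for the primary endpoint.

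The protocol's own default, strata-adjusted logistic regression, is no better at the planned effect. With 25% severe, unadjusted vs adjusted power is 96.5% vs 96.5% at OR 3 and 97.0% vs 96.1% at OR 5. With 10% severe, separation occurred in 8% (OR 1) to 24% (OR 5) of trials. The Mantel-Haenszel interval also covers slightly under 95%.

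All of this is true, and it limits the size of the point. It does not supply the missing evidence on prognosis. It does not justify treating the same failure outcome differently in the Cox and logistic models. The separation problem argues against adjusted logistic regression as primary, but it does not touch CMH. Nor is a weaker effect far-fetched: Protocol 10.1.3 calls the effect highly uncertain, and the historical control rate in 10.1.1 is 71% with a 95% CI of 48% to 89%.

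**Conclusion.** The concern holds and is modest. Both logistic models omit the strata without showing that they are non-prognostic, and the Wald test is conservative to the extent that either is prognostic. With both factors at OR 2 the effect is close to nil. At OR 3 to 5 the power given up is about 0.7 to 1.1 points at the planned effect. At 0.65 vs 0.30 it is about 1.9 to 4.4 points with 25% severe and 1.4 to 2.8 with 10% severe. These are ranges under assumed prevalence, prognostic strength and block size, at N=60. Type I error is not inflated and the sample size is not in error. The terminated trial is unaffected.

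**What to change.** In the prespecified design, or a successor, make a CMH test over the randomization strata primary for loss of response and for the key secondary proportion. Report a Mantel-Haenszel risk difference with a 95% CI. Fix the sparse-stratum rule before unblinding, using counts only; the rule used in the simulations works. Keep the unadjusted logistic model as a sensitivity analysis. If it stays primary, replace the stated reason with one about prognosis.

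The cost is low: the strata are already recorded, and CMH is one added method. If the strata are not prognostic and 10% are severe, CMH over all four strata costs 1.3 points at 0.65 vs 0.30 (80.1% to 78.8%) and 0.5 point at the planned effect (95.5% to 95.0%). The merging rule removes that loss. With other block sizes (2 or 6) and 30% or 70% sensitized, at 25% severe, the largest loss at OR 1 was 0.3 point. The remaining price is the slight undercoverage of the Mantel-Haenszel interval. The SAP for the terminated trial needs no change.

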10.1 Sample Size Estimation

10.1.1 Sample Size Based on the Primary Efficacy Endpoint

The sample size is based on the primary efficacy endpoint of loss-of-response status (binary endpoint of loss-of-response or not), at the End-of-TP2 (ie, within 25 weeks after randomization). The null hypothesis is that there is no difference between C1-INH and placebo with respect to the proportion of subjects with loss-of-response at the End-of-TP2. Let p_0 and p_1 be the expected proportion of subjects with loss-of-response in TP2 in the placebo and C1-INH treatment groups, respectively. The alternative is that there is a difference between the treatment groups. That is, $H_0: p_0 = p_1$ versus $H_1: p_0 \neq p_1$.

The power procedure in SAS STAT software (Cary, NC SAS Institute Inc.) was used to estimate the sample size, based on the likelihood ratio chi-square test. Determination of the sample size was based on the following assumptions:

- The proportions of subjects experiencing loss-of-response at the End-of-TP2 will be 0.75 with placebo and 0.30 with C1-INH.
- There will be at least 90% power to detect a statistically significant effect with two-sided test with alpha = 0.05.
- Logistic regression model with treatment effect will be used for the primary efficacy analysis. Wald test statistic for treatment effect from Logistic regression has approximately same distribution as chi-square [Fleiss et al, 2003]. Therefore, the sample

size calculation based on chi-square test is used to ensure similar power for hypothesis testing.

- Treatment allocation will be 1:1.
- The planned interim analysis for futility will not impact the type 1 error for the final analysis.

Under these assumptions, a total of 60 subjects (30 randomized to C1-INH and 30 randomized to placebo) will provide approximately 95% power. The study will enroll a sufficient number of subjects to ensure that 60 subjects are randomized.

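### The primary decision rule has the wrong sign: it declares efficacy when C1-INH subjects lose response more often than placebo subjects

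*Protocol*

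**What the plan says.** Protocol 10.3.3.1 sets out the primary model and the success rule together.

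- **Event modelled.** π "is the probability that an individual in a given treatment group will have a loss-of-response at the End-of-TP2". Section 10.3.1 defines loss of response as unstable eGFR, allograft failure or death.
- **Model.** logit(π) = α + β_T·X_T, where X_T "is the indicator variable for treatment (C1-INH=1, placebo = 0").
- **Odds ratio.** "The odds ratio for C1-INH versus placebo is" exp(β_T).
- **Success rule.** If H0: β_T = 0 is rejected at the 0.05 level by the Wald test and the point estimate of β_T "is positive, efficacy will be declared".

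Protocol 10.3 gives a general rule on direction: "Statistical significance will be claimed only when the results of the two-sided test favor C1-INH". Protocol 10.1.1 gives the design assumption: "The proportions of subjects experiencing loss-of-response at the End-of-TP2 will be 0.75 with placebo and 0.30 with C1-INH".

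For the key secondary endpoint, all-cause allograft failure at 48 months, Protocol 10.3.3.2 reuses the primary model. SAP 4.2.1.3 repeats the two-sided hypotheses on β_T without any statement about sign. It adds that there will be no formal testing because the study ended early.

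**The concern.** The event is a bad outcome and C1-INH carries the code 1, so a positive β_T means higher odds of losing response on C1-INH than on placebo. The rule names that result as efficacy.

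This is the only success criterion for the primary endpoint. It is also the first step in the serial testing strategy of Section 10.3, so it decides whether the key secondary endpoint is formally tested. Under the sentence taken alone, a drug that works as planned essentially cannot succeed, and one that does the reverse would succeed nearly every time. Read with Section 10.3, the protocol holds two success conditions that cannot both be met: one requires β_T above zero and the other requires it below zero.

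**Working it through.** **Inputs**

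- Loss-of-response rates of 0.75 on placebo and 0.30 on C1-INH, from Protocol 10.1.1.
- 30 subjects per arm and a "two-sided test with alpha = 0.05", from Protocol 10.1.1.
- Event, coding and odds-ratio direction, from Protocol 10.3.3.1.

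**1. Reproduce the stated power.** The plan says "a total of 60 subjects (30 randomized to C1-INH and 30 randomized to placebo) will provide approximately 95% power", based on the likelihood ratio chi-square test.

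- Write e(p) = p·ln p + (1−p)·ln(1−p). The average rate is (0.75 + 0.30)/2 = 0.525.
- Noncentrality = 2 × 30 × [e(0.75) + e(0.30) − 2·e(0.525)] = 12.64 on 1 df, which gives power of 0.945.
- The pooled (Pearson) chi-square gives 0.957.

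Both agree with approximately 95%, so the rates, sample size and alpha are read as the plan intends.

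**2. Sign of β_T at the design rates.**

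- β_T = ln(0.30/0.70) − ln(0.75/0.25) = −0.847 − 1.099 = −1.946
- Odds ratio = exp(−1.946) = 0.143
- Risk difference = 0.30 − 0.75 = −0.45

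The planned benefit is a negative coefficient.

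**3. Probability of each significant result.** All 31 × 31 possible outcomes with 30 per arm were enumerated, each with its exact binomial probability and the two-sided 0.05 Wald test. Where an arm had 0 or 30 events the Wald test is unusable. Fisher's exact test was used there, in place of the exact methods the protocol specifies for non-convergence.

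| True loss rates | Significant, β_T > 0 (rule as printed) | Significant, β_T < 0 (rule corrected) |
|---|---|---|
| Design: C1-INH 0.30, placebo 0.75 | 7.1 × 10⁻⁹ | 0.956 |
| Reversed: C1-INH 0.75, placebo 0.30 | 0.956 | 7.1 × 10⁻⁹ |
| No effect: both 0.525 | 0.026 | 0.026 |
| No effect: both 0.75 | 0.020 | 0.020 |

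The large-sample formula for the Wald test (standard error 0.580, z = −3.35) gives 0.918 and 5 × 10⁻⁸ at the design rates. The level differs a little from the exact figures; the conclusion does not. The stated power belongs to the corrected rule, not the printed one.

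**4. A single result.** Suppose 9/30 lose response on C1-INH and 22/30 on placebo.

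- β_T = ln(9/21) − ln(22/8) = −1.859; odds ratio 0.156
- Standard error = √(1/9 + 1/21 + 1/22 + 1/8) = 0.574; z = −3.24; p = 0.0012

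This is strong evidence of benefit, and the printed rule would not declare efficacy.

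**5. Key secondary endpoint.** Protocol 10.1.2 assumes graft survival of 0.25 on placebo and 0.75 on C1-INH, so failure rates are 0.75 and 0.25. Then β_T = ln(0.25/0.75) − ln(0.75/0.25) = −2.197. Benefit is again negative. The exact probability of a significant negative estimate is 0.985, and of a significant positive one 4 × 10⁻¹⁰.

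**The case against.** No reading of Section 10.3.3.1 makes a positive β_T favorable. That section does refer loosely to the binary outcome as response status, but π is defined explicitly as the probability of loss. The real objections concern consequence and scope.

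- **Intent is clear elsewhere.** Section 10.3 limits claims to results that favor C1-INH, Section 10.1.1 assumes fewer losses on C1-INH, and Section 1.3 expects placebo subjects to lose response. Taken as a whole, the protocol would not let a harmful result be claimed as benefit. This stands: it is most likely a drafting slip, and the 0.956 under reversed rates applies only to the sentence read alone. But nothing says the general rule overrides the specific one.
- **The rule is no longer in use.** The study was terminated with 13 subjects randomized (SAP 3), formal testing was dropped (SAP 4.2.1.3 and 7.3), and the primary endpoint is now reported as proportions with a confidence interval for the difference (SAP 10.1). This stands for the reported result. The protocol sentence nevertheless remains uncorrected.
- **Carry-over to the secondary endpoint is inferred.** Section 10.3.3.2 reuses the model and does not repeat the sign rule, and SAP 10.2 says that analysis cannot be done. This also stands: a statement of direction is needed there, not the correction of a printed error.

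The two-sided type I error and the sample size are unaffected.

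**Conclusion.** The concern holds. The primary success rule is inverted relative to the model it belongs to and contradicts the protocol's own general rule on direction. At the planned rates the printed rule would declare efficacy with probability of about 7 × 10⁻⁹, and the corrected rule with probability 0.956. These figures assume 30 subjects per arm, the design rates as the truth, and the Wald test at two-sided 0.05. The sign conclusion needs none of those assumptions, because it follows from the definitions of π and X_T alone.

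As a matter of the plan this must be fixed, since it is the operative criterion for the primary claim. Because of early termination it does not alter the result to be reported.

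**What to change.** In Protocol 10.3.3.1, reword the success rule to: *If the null hypothesis is rejected at the 0.05 level and the point estimate of β_T is negative (odds ratio below 1), efficacy will be declared.*

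In Protocol 10.3.3.2, add that for all-cause allograft failure, too, a negative coefficient favors C1-INH.

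Since the trial has ended, a documented clarification to the protocol, or a note in the SAP or the clinical study report, is enough. It would keep the sentence from being copied into the report or a later protocol. The change costs nothing in subjects, power or type I error.
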